**Table 19: High-dose Vasopressors (All Doses are Required for ≥3 Hours)**

Therapy	Dose
Norepinephrine monotherapy	≥20 µg/kg/min
Dopamine monotherapy	≥10 µg/kg/min
Phenylephrine monotherapy	≥200 µg/kg/min
Epinephrine monotherapy	≥10 µg/kg/min
If on vasopressin	Vasopressin + NE equivalent of ≥10 µg/kg/min a
If on combination vasopressors (not vasopressin)	Norepinephrine equivalent of ≥20 µg/kg/min a

a VASST Trial Vasopressor Equivalent Equation: Norepinephrine equivalent dose = [norepinephrine (µg/min)] + [dopamine (µg/kg/min) ÷ 2] + [epinephrine (µg/min)] + [phenylephrine (µg/min) ÷ 10]

### 6.8.2. Cytokine Release Syndrome Treatment Guidelines

In the event CRS is observed, vigilant supportive care, including empiric treatment of concurrent bacterial infections and maintenance of adequate hydration and blood pressure is required for every grade. Blood pressure instability will be evaluated in the context of blood pressures obtained at baseline and at Day 1 prior to the ELI-002 vaccine. Appropriate respiratory support will be provided as clinically indicated. Every attempt should be made to discern and treat potentially overlapping symptoms arising from infections, tumor lysis syndrome, or other

medical complications. Blood samples for cytokine and other analysis judged to be appropriate by the investigator will be obtained as soon as possible and daily until clinical concern for CRS has resolved.

The following clinical laboratory parameters will be followed in addition to expeditious local laboratory cytokine analysis:

- C-reactive protein (CRP)
- Complete blood count (CBC) with differential
- Blood chemistries
- Liver function tests
- Ferritin
- Coagulation parameters including prothrombin time, partial thromboplastin time, fibrinogen, D-dimer
- Blood cultures

Tocilizumab must be used as the first-line agent in the treatment of CRS. If the subject's condition does not improve or stabilize within 24 hours of the tocilizumab dose, administration of a second dose of tocilizumab and/or a second immunosuppressive agent (such as corticosteroids) should be considered.

- Tocilizumab is a recombinant humanized anti-human IL-6 receptor monoclonal antibody of the immunoglobulin (Ig) IgG1k subclass. It binds both the membrane bound and soluble forms for the IL-6 receptor, and thus blocks IL-6 mediated pro-inflammatory effects. Tocilizumab is approved for the treatment of CRS occurring in the setting of CAR-T cell therapy, rheumatoid arthritis, systemic juvenile idiopathic arthritis and polyarticular juvenile rheumatoid arthritis [[ACTEMRA® USPI](#)].
- Tocilizumab at a dose of 8mg/kg (max dose 800 mg; or at the level recommended by local standards) should be administered intravenously over 1-hour, with the option to repeat the dose if clinical improvement does not occur within 24 to 48 hours. There should be a minimum of 8 hours between consecutive doses of tocilizumab [[Grupp et al, 2013](#); [Lee et al, 2014](#); [Maude et al, 2015](#)].
- Corticosteroids: Corticosteroids may ablate or significantly impair T-cell function and may limit therapeutic benefit. However, they may be used as a secondary agent or in cases of severe or life-threatening CRS as front-line therapy or in conjunction with Tocilizumab.
- Methylprednisolone (1mg/kg every 12 hours) is recommended, but consideration should be given to using Dexamethasone (10 mg/dose every 6 hours) in subjects with neurologic symptoms who may benefit from more efficient penetration of the blood brain barrier [[Bonifant et al, 2016](#); [Maude et al, 2014](#); [Neelapu et al, 2018](#)].
- Additional agents: Siltuximab (anti-IL6 mAb) [[Chen et al, 2016](#)], Etanercept (soluble TNF $\alpha$  receptor antagonist), Dasatinib (tyrosine kinase inhibitor) [[Mestermann et al,](#)

2019], and Anakinra (IL-1R antagonist) [Giavridis et al, 2018] are investigational but may be considered for use in the context of severe CRS.

Subjects will be advised via the informed consent of the signs and symptoms of CRS. Subjects will be given a protocol-specific card with all necessary information for health care professionals to be aware that the subject is on a clinical trial and to contact the Primary Investigator (PI) and/or team. Subjects will be advised to seek immediate medical attention if such signs and symptoms occur.

Subjects with signs and symptoms of CRS will have blood collected as soon as possible and then at least daily for cytokine and other analysis judged to be appropriate by the investigator until clinical concern for CRS has resolved. Local laboratory cytokine and other appropriate analysis will be undertaken as expeditiously as possible.

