**Table 18: Suggested Treatment by Cytokine Release Syndrome Grade**

Grade	Treatment Requirement	Immunosuppressive Treatment
Grade 1	Symptoms are not life-threatening and require symptomatic treatment only (eg, fever, nausea, fatigue, headache, myalgias, malaise). Vigilant supportive care. Assess for infection, treat fever and neutropenia if present, monitor fluid balance	Acetaminophen and other antipyretics/analgesic supportive measures
Grade 2	Symptoms require and respond to moderate intervention : 
 
• Oxygen requirement <40%
 
• Vigilant Supportive Care
 
	Acetaminophen and other antipyretic/analgesic supportive measures. If multiple comorbidities or older age are present initiate IL-6 inhibition with tocilizumab ± corticosteroids
Grade 3	Symptoms require and respond to aggressive intervention : 
 
• Oxygen requirement ≥40% or
 
• Hypotension requiring at least one vasopressor
 
• Vigilant Supportive Care
 
	Initiate immunosuppressive therapy using tocilizumab and corticosteroids.
Grade 4	Life-threatening symptoms 
 
• Requirement for ventilator support or
 
• Grade 4 organ toxicity (excluding transaminitis)
 
	Initiate immunosuppressive therapy using tocilizumab and corticosteroids
Grade 5	Death	-

High-dose vasopressor doses shown in [Table 19](#).  
[[Lee et al, 2019](#)]

When applicable, use of high-dose vasopressor is recommended as described in [Table 19](#).

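### Protocol Section 6.8.2 requires tocilizumab first-line for CRS at any grade, while Table 18 does not list it at Grade 1 or, without listed risk factors, at Grade 2; the two need reconciling

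*Protocol*

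**What the plan says.** Section 6.8.2 of the protocol opens by requiring supportive care at every CRS grade and then states: "Tocilizumab must be used as the first-line agent in the treatment of CRS". That sentence names no grade. If the subject has not improved or stabilised within 24 hours of the dose, "administration of a second dose of tocilizumab and/or a second immunosuppressive agent (such as corticosteroids) should be considered". A later bullet on corticosteroids permits them as a secondary agent, or "in cases of severe or life-threatening CRS as front-line therapy", or together with tocilizumab.

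Table 18, in Section 6.8.1, is headed "Suggested Treatment by Cytokine Release Syndrome Grade". Its treatment column reads as follows:

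- Grade 1: "Acetaminophen and other antipyretics/analgesic supportive measures", with symptomatic care as the only treatment need.
- Grade 2: antipyretic and analgesic support, and then "If multiple comorbidities or older age are present initiate IL-6 inhibition with tocilizumab ± corticosteroids".
- Grades 3 and 4: "Initiate immunosuppressive therapy using tocilizumab and corticosteroids".

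Section 6.8 says that the trial will follow the guidance in Sections 6.8.1 through 6.8.2. The SAP does not address how CRS is treated.

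**The concern.** A site with a Grade 1 CRS event, or a Grade 2 event in a subject without the listed risk factors, finds two instructions in adjoining sections. One requires an IL-6 receptor blocker. The other stops at supportive care. Nothing in the protocol says which governs.

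The first thing at stake is a safety instruction that sites could apply differently. The second is interpretation of the exploratory pharmacodynamic data. Section 6.2.3 lists serum cytokines, including IL-6, and T-cell immunogenicity as endpoints. Section 6.8.2 itself says that tocilizumab blocks IL-6-mediated effects and that corticosteroids can impair T-cell function. A sample drawn after either drug may therefore not reflect the vaccine alone. Neither SAP Section 13.8.2 nor the immunogenicity and ctDNA addendum provides for identifying such samples.

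**Working it through.** No arithmetic applies and the plan gives no figure to reproduce. The check sets Section 6.8.2 beside Table 18 grade by grade, then looks for any text that limits or ranks them.

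| CRS grade | Section 6.8.2, read literally | Table 18 | Result |
|---|---|---|---|
| 1 | Tocilizumab mandatory | Supportive measures; tocilizumab not listed | Conflict |
| 2, without the listed risk factors | Tocilizumab mandatory | Supportive measures only | Conflict |
| 2, with them | Tocilizumab mandatory | Tocilizumab, with or without corticosteroids | Compatible on tocilizumab |
| 3 and 4 | Tocilizumab first; corticosteroids considered after 24 hours without improvement, or front-line or concurrent if severe | Tocilizumab and corticosteroids started | Agree on tocilizumab; differ on corticosteroid timing and sequence |

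**Does any text rank them?** Section 6.8 adopts both and gives no order of precedence. Table 18 is headed as suggested treatment, but that does not settle the matter: a suggestion cannot relax a mandatory sentence, so a site following the Grade 1 row would still depart from 6.8.2.

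**Does any text limit the mandatory sentence by grade?** No. Section 6.8.2 does state grade scope for supportive care, but not for tocilizumab. The neighbouring ICANS guidance, Section 6.8.3, refers the reader to Table 22 for use of tocilizumab and corticosteroids. Section 6.8.2 has no matching reference to Table 18.

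**What is left at Grades 3 and 4?** The corticosteroid bullet allows both drugs together in severe or life-threatening CRS, which matches the Grade 3 and 4 rows. It also allows corticosteroids front-line. Strictly that departs from the mandatory sentence, but it reads as an express exception within the same section.

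**Is the treatment already recorded?** Yes. Protocol Section 8.1 requires all concomitant medications to be entered in source and eCRF. SAP Section 13.4.4 lists them by subject, and SAP Section 13.7.1 lists CRS data by subject. What is missing is a link from those records to the affected samples.

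**The case against.** The best case against is that the two texts do different jobs. The words in 6.8.2 about a second immunosuppressive agent imply that tocilizumab is the first such agent, so the sentence may only rank drugs, leaving Table 18 to say at which grade immunosuppression starts. This is a natural reading and it would remove the Grade 1 and Grade 2 conflict. It stands as a plausible intention. It does not stand as an answer, because the protocol never states it and the sentence taken alone says otherwise.

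Three stronger conclusions that a reader might draw are not supported:

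- *That the rules cannot all be followed.* The ranking reading shows that they can be. The defect is an unresolved conflict on literal wording.
- *That the choice of first agent in severe CRS is also in contradiction.* The texts agree on using tocilizumab at Grades 3 and 4, and the corticosteroid bullet largely covers the remaining difference.
- *That ordinary vaccine fever would trigger mandatory tocilizumab.* Section 4.6.3 treats fever, myalgia and headache after dosing as expected reactogenicity, which has its own monitoring in Section 12.2.1.3. Section 6.8.2 applies only once CRS is observed and asks sites to discern overlapping causes. The symptoms do overlap with the Grade 1 row, but fever by itself does not invoke the CRS rules.

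It is also fair to say that harm to the endpoints is inferred. The cytokine and T-cell measures are exploratory and summarised by cohort, not by site, and no document shows any distortion between sites.

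**Conclusion.** The point holds for two situations: Grade 1 CRS, and Grade 2 CRS in a subject without several comorbidities or older age. There the mandatory sentence and Table 18, read literally, give different instructions, both in force and neither ranked. At Grades 3 and 4 only a difference in corticosteroid timing and sequence remains, and it is largely bridged.

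The number of events affected cannot be derived; the protocol calls T-cell-mediated toxicity a theoretical risk. A reader might also infer an effect on the MTD, because DLT criteria c and d turn on CRS improving within 7 days or 72 hours. Those criteria concern Grades 3 and 4, where the texts agree on tocilizumab, so any such effect would be a further inference.

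The conclusion rests on the wording of the protocol and on the absence of a clarifying cross-reference in either document. An instruction issued to sites elsewhere could already have settled it. This is a wording inconsistency that should be corrected, and no view is taken on which clinical rule is right.

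**What to change.** - **Protocol.** The sponsor and its clinical advisers should reconcile Section 6.8.2 with Table 18 so that the same rule by grade appears in both places, and add a cross-reference between them. If the mandatory sentence is meant only to rank immunosuppressive agents, it should say so.
- **Sites.** Notify them as applicable. The synopsis gives 2Q2023 for the last enrolment, and Dose 10 falls 160 days after Dose 1 (Day 217 minus Day 57). Dosing was therefore probably complete before SAP Version 3.0 of August 2024. If so, the notice matters less for this trial, but the corrected text would still matter wherever it is reused.
- **Analysis.** Using the concomitant medication data already collected, flag in the listings any cytokine or T-cell sample taken after tocilizumab or corticosteroids, and say in the SAP how flagged samples are shown in the summaries.

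The cost is a wording change, a site memo where still useful, and one derived flag. No new data collection is needed.

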### 6.8.3. ICANS Treatment Guidelines

Neurotoxicity (eg, encephalopathy, somnolence, aphasia; ICANS) has been observed with previous CAR T-cell therapies and since ELI-002 potently activates T cells there is a theoretical risk for ICANS.

Evaluation of any new onset  $\geq$ Grade 2 neurotoxicity should include a neurological examination, brain MRI, and examination of the cerebrospinal fluid (CSF) as clinically indicated.

Endotracheal intubation may be needed for airway protection in severe ICANS cases. Tocilizumab and corticosteroids should be used as outlined in Table 22, and anti-epileptic may be considered as clinically indicated. Medications with sedative properties should be avoided, if possible, in the setting of neurotoxicity. ICANS should be graded in accordance with the ASTCT consensus definitions:

The Immune Effector Cell-Associated Encephalopathy (ICE) scoring system is provided in Table 20, and the current ASTCT ICANS Consensus Grading for Adults is provided in Table 21.

**Table 20: Encephalopathy Assessment Tool for Grading ICANS**

	ICE Scoring System
Orientation	Orientation to year, month, city, hospital: 4points
Naming	Ability to name 3 objects (eg, point to clock, pen, button): 3 points
Following Commands	Ability to follow simple commands (eg, “Show me 2 fingers” or “Close your eyes and stick out your tongue”): 1 point
Writing	Ability to write a standard sentence (eg, “Our national bird is the bald eagle.”): 1 point
Attention	Ability to count backwards from100 by10: 1 point

ICANS=Immune effector cell-associated neurotoxicity syndrome; ICE=Immune Effector Cell-Associated Encephalopathy.  
[Lee et al, 2019]

**Table 21: ASTCT ICANS Consensus Grading for Adults**

Neurotoxicity Domain	Grade 1	Grade 2	Grade 3	Grade 4
ICE Score a	7-9	3-6	0-2	0 (subject is unarousable and unable to perform ICE)
Depressed level of consciousness b	Awakens spontaneously	Awakens to voice	Awakens to tactile stimulus	Subject is unarousable or requires vigorous or repetitive tactile stimuli to arouse. Stupor or coma
Seizure	N/A	N/A	Any clinical seizure focal or generalized that resolves rapidly or nonconvulsive seizures on EEG that resolve with intervention	Life-threatening prolonged seizure (>5 min); or repetitive clinical or electrical seizures without return to baseline in between
Motor findings c	N/A	N/A	N/A	Deep focal motor weakness such as hemiparesis or paraparesis
Elevated intracranial pressure/ cerebral edema	N/A	N/A	Focal/local edema on neuroimaging d	Diffuse cerebral edema on neuroimaging; decerebrate or decorticate posturing; or cranial nerve VI palsy; or papilledema; or Cushing's triad

ASTCT=American Society for Transplantation and Cellular Therapy; CTCAE= Common Terminology Criteria for Adverse Events; ICANS=Immune effector cell-associated neurotoxicity syndrome; ICE=Immune Effector Cell-Associated Encephalopathy; N/A=not applicable

ICANS grade is determined by the most severe event (ICE score, level of consciousness, seizure, motor findings, raised intracranial pressure/cerebral edema) not attributable to any other cause; for example, a subject with an ICE score of 3 who has a generalized seizure is classified as grade 3 ICANS.

a: A subject with an ICE score of 0 may be classified as grade 3 ICANS if awake with global aphasia, but a subject with an ICE score of 0 may be classified as grade 4 ICANS if unarousable.

b: Depressed level of consciousness should be attributable to no other cause (eg, no sedating medication).

c: Tremors and myoclonus associated with immune effector cell therapies may be graded according to CTCAEv5.0, but they do not influence ICANS grading.

d: Intracranial hemorrhage with or without associated edema is not considered a neurotoxicity feature and is excluded from ICANS grading. It may be graded according to CTCAEv5.0.

[Lee et al, 2019]

**Table 22: Neurotoxicity Suggested Treatment**

Neurotoxicity Grading assessment (CTCAE 5.0)	Evaluation	Treatment
Grade 1 – Examples include: Somnolence-mild drowsiness or sleepiness Confusion-mild disorientation Encephalopathy-mild limiting of ADL Dysphasia-not impairing ability to communicate	Neurological examination Additional work up as clinically indicated	Vigilant supportive care
Grade 2 – Examples include: Somnolence-moderate, limiting instrumental ADL Confusion-moderate disorientation, limiting instrumental ADL Encephalopathy-limiting instrumental ADL Dysphasia-moderate impairing ability to communicate spontaneously	Consider EEG as clinically indicated Should include brain MRI and evaluation of CSF in addition to neurological examination	Vigilant supportive care Consider prophylactic anti-epileptic
Grade 3 – Examples include: Somnolence-obtundation or stupor Confusion-severe disorientation, limiting self-care ADL Encephalopathy-limiting self-care ADL Dysphasia-severe receptive or expressive characteristics, impairing ability to read, write or communicate intelligibly		Consider tocilizumab 4-8 mg/kg IV over 1 hour (not to exceed 800 mg) Repeat tocilizumab if symptoms have not stabilized or improved within 12-24 hours Consider corticosteroids (eg, dexamethasone 10 mg IV q6h) for worsening symptoms despite tocilizumab Consider prophylactic anti-epileptic
Grade 4 – Examples include: Life-threatening consequences Urgent Intervention Indicated Mechanical Ventilation		Corticosteroids (eg, dexamethasone 10 mg IV q6h) Administer tocilizumab as per guidance for Grade 3 neurotoxicity if not previously administered Consider prophylactic anti-epileptic

ADL=activities of daily life; CSF=cerebrospinal fluid; CTCAE= Common Terminology Criteria for Adverse Events; EEG=electroencephalogram; IV=intravenous; MRI=magnetic resonance imaging

#### 6.8.4. Management of On-target Off-tumor Toxicity

Examples of on-target off-tumor toxicities have been observed in different immunotherapies where these events were not expected from pre-clinical data. It is difficult to anticipate all “autoimmune inflammation” that theoretically may be induced by an on-target off-tumor effect of ELI-002. For that reason, Grade 3 or higher autoimmune toxicity is considered a DLT (ie, fits non-hematologic ≥Grade 3 toxicity; see [Section 6.7.3](#)) Any observed treatment emergent autoimmune events must be followed closely. The exact diagnostic and the therapeutic approach to be followed will be left to the investigator’s discretion who can contact at any time the Sponsor Medical Monitor. The Sponsor may discuss any specific case with the SMC members to evaluate appropriate therapeutic action.

#### 6.8.5. Management of Maculo-Papular or Acneiform Rashes, Injection Site Reactions

For routine injection site reactions manifested as maculo-papular or acneiform rashes, erythema, induration, pruritis and pain, topical application of cool compresses, antihistamine or corticosteroids may be used. If needed, systemic antihistamines and antipyretics may be added.

## 7. SELECTION AND WITHDRAWAL OF SUBJECTS

### 7.1. Subject Inclusion Criteria

Subjects must meet the following criteria on screening examination to be eligible to participate in the trial:

1. Male or female subjects aged  $\geq 18$  years
2. Histologically or cytologically confirmed diagnosis of solid tumor
3. Depending on the clinical site ability to access acceptable tumor sample for analysis: available tumor sample and EDTA blood sample for central lab WES biomarker analysis (preferable) or a blood sample for central lab plasma RAS ctDNA assay, which demonstrates at least 1 of the 2 mKRAS/NRAS alleles (eg, G12D or G12R) targeted by ELI-002 2P
4. High relapse risk, as evidenced by biomarker data with the last value obtained  $\geq 21$  days after surgery or last administration of adjuvant therapy, whichever comes last in the specific subject's treatment plan (values must not be attributable to a non-cancer condition, such as pancreatitis, peritonitis, postoperative leak/fistula, or biliary obstruction) as follows:
  - a. ctDNA blood test positive, or
  - b. successive rising values ( $\geq 1$  week apart) in a serum tumor biomarker (such as CA19-9, CEA, and CA-125), or
  - c. individual biomarker values CA19-9  $\geq 90$  U/mL, or CEA  $\geq 15$  ng/mL, or CA-125  $\geq 35$  U/mL
5. If subject has PDAC:
  - a. Stage I, II, III or Stage IV oligometastatic ( $< 3$  lesions in one organ) disease per current American Joint Committee on Cancer (AJCC) staging criteria, with radiographic NED (no evidence of disease) status following surgery. Equivocal radiographic findings (eg, subcentimeter lesions, potential resolving soft tissue changes after surgery) are acceptable.
  - b. Prior treatment with a standard of care chemotherapy or chemotherapy/chemoradiation (eg, FOLFIRINOX, gemcitabine/nab-paclitaxel, or 5-FU/capecitabine) according to NCCN pancreatic cancer guidelines and administered in neoadjuvant and/or adjuvant setting
  - c. Successful surgical resection (focal use of intraoperative irreversible electroporation (eg, Nanoknife®) is permitted): Complete resection (R0) or with microscopic residual disease (R1)
6. If subject has CRC:
  - a. High risk Stage II (T4N0), Stage III (T4N1-2/TanyN2), or Stage IV oligometastatic disease per current AJCC staging criteria, with radiographic NED status following surgery. Equivocal radiographic findings (eg, subcentimeter lesions, potential resolving soft tissue changes after surgery) are acceptable.

- b. Prior treatment with standard of care chemotherapy (eg, FOLFOX, CAPEOX) according to NCCN colon cancer guidelines and administered in neoadjuvant and/or adjuvant setting
    - c. If the subject has rectal cancer, prior treatment with standard of care chemoradiation (eg, 5-FU or capecitabine- based) according to NCCN rectal cancer guidelines and administered in the neoadjuvant or adjuvant setting, or as total neoadjuvant therapy
    - d. For non-rectal subjects, successful surgical resection (focal use of intraoperative irreversible electroporation (eg, Nanoknife®) is permitted): Complete resection (R0) or with microscopic residual disease (R1)
7. If the subject has NSCLC Stage IB, II, or III disease per current AJCC staging criteria (8th edition) with receipt of stage-appropriate standard of care therapy per NCCN guidelines. The criteria below are examples of current common clinical scenarios based on stage. Since some agents are recently approved for specific clinical settings, alternative historical standard of care regimens will be allowed with approval of the medical monitor.
  - a. Stage IB (T3-T4): complete surgical resection (R0). Prior systemic therapy is not required.
  - b. Stage II:
    - i. neoadjuvant SOC platinum-based chemotherapy according to NCCN guidelines with checkpoint inhibitor (if the tumor is  $\geq 4$  cm or node positive), followed by complete surgical resection (R0)
    - ii. complete surgical resection (R0), followed by adjuvant chemotherapy with a SOC platinum doublet (eg, cisplatin/pemetrexed, cisplatin/gemcitabine, cisplatin/docetaxel, cisplatin/vinorelbine, or carboplatin/paclitaxel) and checkpoint inhibitor (if the tumor is  $>1\%$  PDL1+) according to NCCN guidelines
  - c. Resectable Stage III:
    - i. Prior standard of care neoadjuvant platinum-based chemotherapy:
      - a) with or without checkpoint inhibitor (if the tumor is  $\geq 4$  cm or node positive), followed by complete surgical resection (R0)
      - b) with or without radiation, followed by complete surgical resection (R0), followed by checkpoint inhibitor (if the tumor is  $>1\%$  PDL1+)
    - ii. Complete surgical resection (R0) followed by SOC adjuvant platinum-based chemotherapy (with or without radiation for N2 disease) followed by a checkpoint inhibitor (if the tumor is  $>1\%$  PDL1+) according to NCCN guidelines
  - d. Unresectable Stage III: concurrent standard of care chemotherapy and radiation followed by consolidation with checkpoint inhibitor regardless of PDL1 expression
  - e. Equivocal radiographic findings (eg, subcentimeter lesions, potential resolving soft tissue changes after surgery) are acceptable.
8. If subject has ovarian cancer:
  - a. Stage II, III or IV disease per current AJCC staging criteria, including ovarian, fallopian tube and primary peritoneal cancers or borderline tumors  
Primary debulking surgery with optimal cytoreduction (residual disease  $<1$ cm [R1] or removal of macroscopic disease [R0]) followed by six cycles of standard of care platinum-based adjuvant chemotherapy (eg, paclitaxel 175/carboplatin or pyrimidine-

based 5-FU/leucovorin/oxaliplatin or capecitabine/oxaliplatin) or neoadjuvant standard of care platinum-based chemotherapy with interval debulking surgery for subjects who were not candidates for primary debulking surgery due to disease unlikely to be optimally cytoreduced, followed by standard of care adjuvant platinum or pyrimidine based chemotherapy (eg, paclitaxel 175/carboplatin, or 5-FU/leucovorin/oxaliplatin or capecitabine/oxaliplatin). Equivocal radiographic findings (eg, potential resolving soft tissue changes after surgery) are acceptable.

9. If subject has CCA or gallbladder carcinoma:
  - a. Localized and surgically resected intrahepatic, perihilar or distal CCA, or surgically resected gallbladder carcinoma (focal use of intraoperative irreversible electroporation (eg, Nanoknife®) is permitted) with complete resection (R0) or microscopic residual disease (R1). Equivocal radiographic findings (eg, subcentimeter lesions, potential resolving soft tissue changes after surgery) are acceptable.
  - b. For subjects with CCA and R0 resection, observation or standard of care adjuvant treatment or chemoradiation per the list below; for CCA and R1 resection, standard of care adjuvant treatment or chemoradiation per the list below
  - c. For subjects with gallbladder carcinoma (with either R0 or R1 resection), standard of care neoadjuvant, adjuvant or chemoradiation per the list below

Neoadjuvant (gallbladder only) eg, 5-FU oxaliplatin, capecitabine oxaliplatin, gemcitabine capecitabine, gemcitabine cisplatin, 5-FU cisplatin, capecitabine cisplatin, gemcitabine cisplatin nab-paclitaxel, gemcitabine oxaliplatin, 5-FU, capecitabine, gemcitabine

Adjuvant, eg, capecitabine, 5-FU oxaliplatin, capecitabine oxaliplatin, gemcitabine capecitabine, gemcitabine cisplatin, 5-FU cisplatin, capecitabine cisplatin, 5-FU, gemcitabine (gallbladder and intrahepatic CCA only)

Chemoradiation, eg, XRT with 5-FU, XRT with capecitabine

10. Screening CT is negative for recurrent disease

11. Laboratory values must be:

- a. Absolute neutrophil count  $\geq 1.5 \times 10^9/L$
- b. Platelets  $\geq 100 \times 10^9/L$
- c. Hemoglobin  $\geq 9$  g/dL
- d. Total bilirubin  $\leq 1.5 \times$  ULN, unless subject has documented Gilbert's syndrome
- e. Aspartate aminotransferase (AST) or alanine aminotransferase (ALT)  $\leq 2.5 \times$  ULN
- f. Serum creatinine  $< 1.5$  mg/dL (or if serum creatinine is  $\geq 1.5$  mg/dL, the creatinine clearance calculated by Cockcroft-Gault formula must be  $\geq 60$  mL/min)
- g. Albumin  $\geq 2.5$  g/dL
- h. IL-6  $< 500$  pg/mL

12. Eastern Cooperative Oncology Group (ECOG) performance status of 0 or 1

13. Subjects have recovered from prior surgery, chemotherapy, or radiation without any ongoing medical/surgical issues (excluding resolved, low grade or chronic stable findings such as neuropathy, impaired hearing, or reproductive changes)

14. Women of childbearing potential and men with a female partner of childbearing potential must be willing to use effective methods of contraception during trial participation and for 30 days after the last dose of trial drug to prevent pregnancy as follows:
  - a. Women: willing to use contraceptives with a failure rate <1% per year when used consistently and correctly, eg, combined oral contraceptives, barrier methods, approved contraceptive implant, long- term injectable contraception, or intrauterine device, sexual abstinence, or a vasectomized partner  
  
Definitions that meet the criteria to not be considered of childbearing potential:
    - Women >2 years postmenopausal (defined as 1 year or longer since last menstrual period) AND >55 years of age
    - Postmenopausal women (as defined above) and <55 years of age with a negative pregnancy test within 24 hours of first dose
    - Women who were surgically sterilized at least 3 months prior to enrollment
  - b. Men: willing to use an acceptable method of birth control, eg, condom with spermicide. In addition, men must refrain from donating sperm.
15. Able to provide written (signed) informed consent to participate in the trial prior to any trial specific screening procedures

